8 RESEARCH QUESTION AND OBJECTIVES

The overall goal of this study is to perform an effectiveness evaluation of the ENJAYMO™ Physician's Guide among HCPs who treat patients with CAD. Specific objectives are described in [Sections 8.1](#) and [8.2](#).

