To endeavor to achieve a sample of at least 50 completed surveys, recruitment will remain open for a minimum of 3 months and up to 6 months in each country, and will not be closed early even if 50 completed surveys have been reached sooner. Metrics will be tracked to monitor survey progress (e.g., number of eligible/ineligible HCPs, number of completed surveys). Depending on response rates, follow-up reminders will be sent to non-respondents to achieve the target sample size. If after two reminders the target sample size has not been reached, the pool of potential HCP prescribers will be supplemented through additional outreach based on internet research or outreach through applicable professional societies, inclusion of additional countries within the European Union (EU)/European Economic Area (EEA), or extension of the survey period. The local teams of medical scientific liaison from Sanofi may also support the survey by reaching out to some of the HCPs contacted and whom they may already know or visit, so to encourage their participation.

The survey may be conducted in up to 2 waves. In the event that the survey has been open for 6 months in all countries and 30 completed surveys have not been achieved, with a minimum

of 10 of those having been completed by ENJAYMO™ prescribers, a second wave of the same survey will be conducted 6 to 12 months later.

Invitations to participate in the survey may be sent to up to 1,000 HCPs by either email (preferred) or by post mail (if email is not available) using the available contact information. The invitation letter will include information about the survey, a unique code, and instructions for accessing the survey. The unique code will be used to track who has already completed a survey so that reminders are only sent to HCPs who have not yet completed the survey.

As an acknowledgement of their time and valuable input, HCPs who complete the survey will receive fair market value (FMV) compensation if allowed, feasible, and in accordance with local regulations.

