	Knowledge of current local vaccine guidelines or recommendations in patients with persistent complement deficiencies	Checked “true” to question 5
Knowledge of important potential risks of serious infections from encapsulated bacteria	Knowledge that Neisseria meningitides infection warrants caution	For question 6: “Checked” Neisseria meningitides infection warrants caution
	Knowledge that Hemophilus influenza infection warrants caution	For question 6: “Checked” Hemophilus influenza infection warrants caution
	Knowledge that Streptococcus pneumoniae infection warrants caution	For question 6: “Checked” Streptococcus pneumoniae infection warrants caution
	Knowledge that urinary tract infection warrants caution	For question 6: “Checked” urinary tract infection warrants caution
HCPs’ knowledge of the need to monitor and counsel patients	Knowledge to monitor for signs and symptoms of serious infections	Checked “yes” to question 7b
	Knowledge of caution in patients with chronic infections (Hep B, C or HIV)	Checked “yes” to question 7c
	Knowledge to counsel patients about the risks including meningitis	Checked “yes” to question 7d
	Knowledge that monitoring for kidney damage is not indicated	Checked “no” to question 7a
	Knowledge that thyroid function does not need to be assessed	Checked “no” to question 7e
	Knowledge that patients do not need to be counselled to monitor heart function	Checked “no” to question 7f
HCPs’ knowledge to counsel patients to monitor for symptoms of relevant serious infections	Knowledge to counsel patients to seek	Checked “false” to question 8c
	Knowledge that swelling in legs, ankles and feet is not a symptom of interest	Checked “false” to question 8e
	Knowledge that polyuria, dry mouth and blurred vision is not a symptom of interest	Checked “false” to question 8f
Assess whether HCPs received and read the ENJAYMO™ Physicians’ Guide	Received ENJAYMO™ Physician’s Guide	Checked “yes” to question 1
	Read ENJAYMO™ Physician’s Guide	Checked “yes” to question 2
Primary source of the indication, risk and	Response choices: SmPC, ENJAYMO™ Physician’s Guide, Professional society or	Checked each of the response choices to question 9

Study Objective Domains Assessed	Corresponding variable	Operational definition/derivation “Calculated as the percentage of HCPs who”*
recommendations for ENJAYMO™	congress, EMA website, Clinical practice guidelines, Other	

*Denominator to include “I don’t know/am not sure”

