9.3 Study Design

This is a multinational, non-interventional, cross-sectional survey study to evaluate the effectiveness of the ENJAYMO™ Physician's Guide among EEA-based HCPs.

The current study is planned to be conducted among HCPs in countries in the EEA where the product is expected to be commercially available for at least 6 months. The survey will be launched no sooner than 6 months, and no longer than 18 months, after the ENJAYMO™ Physician's Guide has been disseminated in each participating country. Countries may include Austria, Germany, Italy, and the Netherlands. A convenience sample of HCPs will be recruited from the target population of HCPs who treat patients with CAD and may prescribe ENJAYMO™ in these countries.

The survey is anticipated to be open between 3 to 6 months per country per wave. Depending on response rates, follow-up reminders will be sent to non-respondents to endeavor to achieve the target sample size, and the medical scientific liaison team of Sanofi may also be involved in some countries to advocate for the participation in the survey through their personal contacts with HCPs already contacted via e-mail. In the event that less than 30 completed surveys are achieved in the first wave of the study, a second wave of the same survey will be triggered.

Data will be collected by web-based electronic data capture. Information collected will include the receipt and reading of the ENJAYMO™ Physician's Guide, knowledge of the key information included in the ENJAYMO™ Physician's Guide, the impact of the ENJAYMO™ Physician's Guide on clinical action, and HCP characteristics.

All data will be maintained in compliance with local regulations. Results will be analyzed using SAS. Results will be summarized in tables and figures (as applicable). A statistical analysis plan will be developed to describe the planned statistical analyses in detail and finalized prior to the end of data collection. A final study report will be prepared.

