9.9.1.2 Statistical Methods

Data analysis will be performed by ICON qualified personnel in accordance with ICON's SOPs for statistical analysis and programming. All analyses will be performed using appropriate statistical software (e.g., SAS[®] Version 9.0 or later). A report summarising the results of the survey will be developed.

The primary criteria is the composite knowledge level for the core question set. The composite will be an opportunity/denominator based weighted percentage of HCPs who have answered each item correctly (if at least 30 HCPs have completed the item).

Other criteria include measures of receipt and reading of the ENJAYMO™ Physician's Guide, knowledge levels for each question regarding the information included in the ENJAYMO™ Physician's Guide (i.e., all questions relating to all domains), assessed as the percentages of HCPs with correct responses to each question, the distribution of HCPs' responses regarding their experience with patients' receptivity to vaccination and the implementation of vaccination (date of vaccination versus treatment start, if the prescriber administered the vaccinations), and the distribution of responses regarding the primary source(s) from which HCPs learned about the information included in the ENJAYMO™ Physician's Guide.

Descriptive data analyses will be conducted for all primary and secondary objectives. Descriptive statistics for continuous data will include N, means, and standard deviations. Results for some continuous variables may include ranges (minimums and maximums) and medians as well. Categorical data will be summarised using frequency counts and percentages. Knowledge levels will be calculated with 95% 2-sided CI. Knowledge levels will also be stratified by items with potential to confound the knowledge level (e.g., country, specialty, reads/uses vs. did not read/does not use the ENJAYMO™ Physician's Guide,

prescribing status). Missing data will be reported, but no replacement or imputation will be performed.

For each primary endpoint, the weighted average percentage of HCPs who answered the core question set correctly will be estimated and assessed against the 80% (\pm 95% CI) target (if the number of HCPs who answered the item is at least 30).

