B	Monitor patients for signs and symptoms of serious infections			
C	Take caution when prescribing ENJAYMO™ to patients who have chronic infections such as Hepatitis B, Hepatitis C or HIV			
D	Counsel patients about the risks of serious infection including meningitis			
E	Monitor patients for thyroid function			
F	Counsel patients about the risks of abnormal heart function			

8. According to recommendations in the “**ENJAYMO™ Physician’s Guide**,” you should counsel patients to seek immediate medical attention if they experience symptoms associated with risks of serious infections or meningococcal infections associated with ENJAYMO™ (sutimlimab). Please answer “True”, “False” or “I don't know/am not sure” to the following symptoms:

		True	False	I don't know/am not sure
A	Headache with stiff neck or back or confusion			
B	Fever, chills and rash			
C	Loss of appetite			
D	Muscle aches with flu-like symptoms			
E	Swelling in legs, ankles and feet			
F	Polyuria, dry mouth and blurred vision			

9. What is (are) the **primary source(s)** you use to learn about the appropriate indication, precautions for use, and potential risks for ENJAYMO™ (sutimlimab)? Please select all that apply. There are no correct/incorrect answers: **SELECT ALL THAT APPLY ANSWER – NO CORRECT RESPONSE.**

- Summary of Product Characteristics
- ENJAYMO™ Physician's Guide
- Professional Society or Congress
- The European Medicines Agency website
- Via specific discussions with Sanofi MSL
- Clinical practice guidelines; specify: _____
- Other (not listed above); specify: _____

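### Sponsor medical liaisons may prompt selected HCPs to respond while the survey is open, with no limit on content, no contact flag and no mention in the limitations, which leaves open an upward bias of unknown size

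*Protocol*

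**What the plan says.** Section 9.1.1 (Main Survey) states that "The local teams of medical scientific liaison from Sanofi may also support the survey by reaching out to some of the HCPs contacted", and describes these HCPs as people "whom they may already know or visit, so to encourage their participation". Section 9.3 (Study Design) says that "the medical scientific liaison team of Sanofi may also be involved in some countries to advocate for the participation in the survey", and that this happens through personal contacts with HCPs who have already been e-mailed. The Synopsis carries an equivalent sentence. The contact is therefore selective, differs between countries, and falls after invitation while the survey is open.

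In Annex 3, question 9 asks for the primary sources from which the respondent learns about the indication, precautions and risks. One of its seven options is "Via specific discussions with Sanofi MSL". Table 9-1, which defines the endpoint built on question 9, lists six choices. Its list ends with "congress, EMA website, Clinical practice guidelines, Other" and contains no liaison option.

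The analysis pools all respondents and compares the composite with 80% (Sections 9.2.1 and 9.9.1.2). Section 8 frames the purpose as follows: "The overall goal of this study is to perform an effectiveness evaluation of the ENJAYMO™ Physician's Guide among HCPs who treat patients with CAD".

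**The concern.** The sponsor's liaisons have two roles here: they may recruit respondents, and the questionnaire recognises them as a source of the knowledge being scored. Two mechanisms follow, and both probably push scores upward.

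- **Selection.** HCPs whom the liaisons already know or visit are probably more engaged with the product than other invitees. Adding them shifts the respondent mix.
- **Information.** A conversation shortly before the survey may touch on the product's risks or prompt a late reading of the Guide. Nothing in the protocol rules this out.

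With no comparator group, a score raised by either route cannot be told apart from knowledge gained from the Guide. Because liaison support is limited to some countries, it could also distort comparisons between the country strata. If contact is not flagged during fieldwork, no later analysis can recover it.

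**Working it through.** **1. What the protocol records and controls**

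| Question | What the protocol provides |
|---|---|
| Is liaison contact allowed while the survey is open? | Yes, for some HCPs in some countries (9.1.1, 9.3) |
| Stated purpose | Participation only (9.1.1, 9.3) |
| Limit on content | None. The safeguard in 9.8 covers looking up answers or discussing the survey during completion, not beforehand |
| Variable that marks the contact | None in Table 9-1, Table 9-2 or Annex 3. The unique code in 9.1.1 is used to track completion and direct reminders |
| Stratification | "Knowledge levels will also be stratified by items with potential to confound the knowledge level (e.g., country, specialty"; reading or use of the Guide and prescribing status are also named. Liaison contact is not, although the list is given as examples |
| Limitations | 9.11 discusses selection bias in general. Liaison contact is not mentioned |
| Time check | 9.11 stratifies by time since distribution of the Guide, which cannot show a recent liaison contact |
| Self-report | Question 9 records liaison discussions as a source, but neither dates them nor links them to survey outreach |

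**2. Question 9 in two places**

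Annex 3 has seven options, and the programming note randomises the first five, of which the liaison option is the fifth. Table 9-1 has six choices without it. The two lists contradict each other on a stated secondary endpoint.

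**3. The plan's own precision figure**

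Inputs from Section 9.7: n = 50, knowledge level 80%, two-sided 95% CI, simple asymptotic formula.

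Half-width = 1.96 × √(0.80 × 0.20 / 50) = 0.1109, or 11.1 points. This reproduces the stated figure. It describes sampling error only and makes no allowance for bias.

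**4. How large the shift could be (assumptions only)**

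The protocol gives no share contacted, no gain and no baseline. Let b be the level without contact, f the share of respondents contacted, and u the amount by which contacted respondents score higher. Then:

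expected level = b + f × u, and shift = f × u.

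- f = 20%, u = 10 points: shift = 2 points.
- f = 40%, u = 10 points: shift = 4 points.
- From an assumed b = 77%, these give 79% and 81%. Reaching 80% needs f = (80 − 77)/10 = 30%.
- Wider range: f = 10%, u = 5 gives 0.5 points; f = 50%, u = 20 gives 10 points.

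One scenario for a single item with 50 answers: b = 75%, f = 30%, u = 15 points gives an expected 75 + 0.30 × 15 = 79.5%. The binomial probability of at least 40 of 50 correct is 26% at 75% and 55% at 79.5%.

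**5. What a with/without comparison could show**

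If 40% of 50 were contacted, 50 − 20 = 30 remain. By the formula in step 3, the half-width at 80% is 1.96 × √(0.16/30) = 14.3 points for the 30 and 1.96 × √(0.16/20) = 17.5 points for the 20. The comparison is descriptive at best.

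**The case against.** The strongest reply is that the protocol gives participation as the only purpose and nowhere provides for liaisons to discuss the Guide, the risks or the questions. That is correct. A reader might infer that respondents are to be coached just before the test. The documents do not support this: listing liaisons in question 9 as a general source of product information says nothing about what a recruitment contact contains. An information effect is a possibility left open, not a planned activity.

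A reader might also infer that liaison exposure goes wholly unrecorded, or that the gap in Table 9-1 loses the data. Neither holds. Annex 3 collects the option from each respondent, so results could be split by it; questions 20 and 21, on trial and registry involvement, give a further rough indication of ties to the sponsor. What stands is that none of these items identifies or dates the survey outreach.

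Other points have partial force:

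- The strata are only examples, and Section 9.8 sends further data-collection detail to the survey manual and SAP. A script or log may exist there, so the finding is limited to what the protocol itself fixes.
- Section 9.11 already names selection bias from the convenience sample and low response as a primary limitation. It does not name this route.
- Liaison encouragement may reduce non-response where only 5% is expected, so its net effect on selection is not certain to be harmful.
- The survey is descriptive, has no prior hypothesis, and expects knowledge to come from several sources. It nevertheless sets an 80% success criterion and is presented as an evaluation of the Guide.

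**Conclusion.** The point holds as a gap in safeguards. The protocol permits selective, country-dependent contact by sponsor liaisons while the survey is open. It does not limit the content, mark the contact or acknowledge it, and it judges an uncontrolled pooled score against 80%. An upward bias through selection, and possibly through information, is therefore possible and could not be separated out from the variables the protocol specifies.

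Its size is unknown. The 2–4 point shift depends entirely on an assumed 20–40% contacted and an assumed 10-point gain. At the lower end, a 77% baseline stays below 80%. The figures show only that a result near the threshold could be moved; they do not predict that it will be.

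The mismatch between Table 9-1 and Annex 3 is a plain contradiction and needs correcting whatever view is taken of the bias.

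**What to change.** - **(a)** In Sections 9.1.1 and 9.3, and in the matching Synopsis text, limit liaison contact between invitation and survey close to a neutral request to take part, with no discussion of the Guide, the product's risks or the survey content.
- **(b)** Flag each liaison contact against the HCP's existing unique code.
- **(c)** Report the composite by contact status, and again without contacted respondents, as a descriptive sensitivity analysis. State that the 30-respondent success rule does not apply to it, because excluding 40% of 50 would leave exactly 30 and one missing answer would take an item below the minimum. Name the issue in Section 9.11.
- **(d)** Add "Via specific discussions with Sanofi MSL" to the question 9 response choices in Table 9-1, so that the table matches Annex 3.

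The cost is some bookkeeping during fieldwork, one extra table and one corrected row. Outreach may be slightly less persuasive, and the contacted subgroup will be small and imprecise. Items (a) and (b) must be in place before liaison outreach begins, because contact that was not logged cannot be reconstructed.

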9.1.2 Language Considerations

The survey questionnaire, HCP agreement and invitation letter will be translated to the local language for each country. To ensure that the questionnaire is easily understandable and conceptually equivalent in the local language, the linguists will align specific phrases with those used in the ENJAYMO™ Physicians Guide from each country. Translations will be independently proof-read by linguists and then reviewed and approved by a local Sanofi affiliate in each of the participating countries. These local Sanofi affiliate team members will be required to sign a validation of review that will be kept in the trial master file.

9.2 Endpoints

The survey includes a survey introduction and screening questions to ensure the HCP is eligible to participate in the survey. The main survey questions are described in [Sections 9.2.1](#) and [9.2.2](#), and in Table 9-1 and 9-2.

9.2.1 Primary

The primary endpoint is knowledge levels of key information included in the ENJAYMO™ Physician's Guide across these 4 domains (assessed by 6 questions):

- Indication for CAD patients only (question 3)
- Important potential risks of serious infections including meningococcal infections (questions 4 and 6)
- Recommendations for vaccination of patients as per local regulations (question 5)
- Recommendations for monitoring and counseling patients to promote real-world safe-use conditions (questions 7 and 8).

The primary endpoint is a composite endpoint based on the percentages of HCPs with correct responses to questions included in the composite. The composite is the weighted average knowledge level across the core question set (6 questions) from the above domains. Success

criteria for the primary endpoint percentage is at least 80% of HCPs have answered the item correctly (if the number of HCPs who answered is at least 30).

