100	9.6	50.4, 69.6	9.0	61.0, 79.0	7.8	72.2, 87.8	5.9	84.1, 95.9

Note: Calculated using PASS 12 software,* confidence intervals for 1 proportion, simple asymptotic formula.

* Hintze, J. (2014). PASS 12. NCSS, LLC. Kaysville, Utah, USA. www.ncss.com.

Data Analysis:

The primary analysis population will include all HCPs who have completed at least 1 of the primary effectiveness endpoint questions on the survey. The primary criteria is the weighted percentage of HCPs with correct responses to the key question set.

In the event that the study is conducted in 2 waves, HCP responses from both waves will be combined to comprise the primary analysis population.

Other criteria include measures of receipt and reading of the ENJAYMO™ Physician's Guide, knowledge levels for each question regarding the information included in the ENJAYMO™ Physician's Guide (i.e., all questions relating to all domains), assessed as the percentages of HCPs with correct responses to each question, the distribution of HCPs' responses regarding their experience with patients' receptivity to vaccination, and the distribution of responses regarding the primary source(s) from which HCPs learned about the information included in the ENJAYMO™ Physician's Guide.

[figure not shown]
All analyses will be performed using appropriate statistical software (e.g., SAS® Version 9 or later). Data analyses will be descriptive. For continuous variables, counts, means (with standard deviations), medians (with interquartile ranges, minimum, and maximum) will be provided. For categorical variables, frequencies and percentages (with 95% CI) will be provided. Missing data will be reported, but no replacement or imputation will be performed.

Knowledge levels will be calculated with 95% 2-sided CI. Knowledge levels will also be reported by relevant subgroups (e.g., country, prescribers vs. potential, reads/uses vs. did not read/does not use the ENJAYMO™ Physician's Guide).

For each primary endpoint, the weighted average percentage of HCPs who answered all the questions in the core question set correctly will be estimated and assessed against the 80% (\pm 95% CI) target (if the number of HCPs who answered all questions is at least 30).

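### The 80% success rule for the primary endpoint is stated inconsistently: a weighted average over six questions in most places, an all-questions-correct share in the synopsis analysis, and a confidence interval with no stated role

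*Protocol*

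**What the plan says.** Section 9.2.1 names six core questions (3 to 8) in four domains and says: "The composite is the weighted average knowledge level across the core question set (6 questions) from the above domains". Section 8.1 and the endpoint part of the synopsis describe the same weighted composite.

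The success sentence that follows in 9.2.1, repeated in the synopsis, requires that "at least 80% of HCPs have answered the item correctly", provided at least 30 HCPs answered. It does not say whether one item, each item or the pooled items must reach 80%.

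Section 9.9.1.2 describes the composite as "an opportunity/denominator based weighted percentage of HCPs who have answered each item correctly (if at least 30 HCPs have completed the item"). It later refers to the weighted average percentage of HCPs "who answered the core question set correctly will be estimated and assessed against the 80"% target, with ± 95% CI in brackets after the figure.

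The parallel sentence in the synopsis, under Data Analysis, applies the same target to the "weighted average percentage of HCPs who answered all the questions in the core question set correctly", on condition that it holds "if the number of HCPs who answered all questions is at least 30".

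Both analysis sentences open as if there were several primary endpoints. The protocol has one composite.

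**The concern.** An average of question-level percentages and the share of HCPs with every question right are different estimands. The second can never exceed the percentage correct on the hardest question, and it usually lies well below the average. A per-item rule lies between the two. If the interval takes part in the decision, the bar moves again. The minimum of 30 also changes its base: HCPs who answered (9.2.1), HCPs who completed the item (9.9.1.2), or HCPs who answered all questions (synopsis).

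The 80% target is the study's only success criterion, and the result goes to EMA as the effectiveness evaluation of the risk minimisation measure. As written, a reader can support either a pass or a fail from the same answers by choosing the sentence.

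**Working it through.** **1. The plan's own precision figure.** Inputs from section 9.7 and Table 9-3: n = 50, p = 0.80, simple asymptotic two-sided 95% interval.

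Half-width = 1.96 × √(0.80 × 0.20 / 50) = 0.111, so the CI is 68.9% to 91.1%. This reproduces the stated 11.1% and interval. The case passes if the point estimate decides (80% ≥ 80%) and fails if the lower limit decides (68.9% < 80%).

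For a single proportion at n = 50, the lower limit first reaches 80% at 45/50: 90% observed, lower limit 81.7%, as in the table's own 90% cell. At 44/50 it is 79.0%. The role of the interval therefore moves the bar from 80% to 90% observed. These cut-offs are for one yes/no proportion. The composite averages six answers per HCP, so they carry over only approximately.

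**2. One data set, several verdicts.** Illustrative assumption: 50 HCPs, no missing answers, correct counts 47, 46, 45, 44, 40, 35, that is 94, 92, 90, 88, 80 and 70%.

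- Weighted average: Σ correct / Σ answered = 257/300 = 85.7%. Pass on the point estimate.
- Every question at 80% or more: the last is at 70%. Fail.
- All six correct, upper bound: the lowest question percentage, 35/50 = 70%. Fail whatever the pattern of answers.
- All six correct, lower bound: 1 − (3 + 4 + 5 + 6 + 10 + 15)/50 = 1 − 43/50 = 14%. Under independence the share is 38.4%.
- Lower 95% limit of the composite: 76.0% with n = 50 (fail), or 81.7% with the 300 answers treated as independent (pass).

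**3. Equal knowledge on all six questions.** Assumption: each question is 90% correct. The average is 90%. The all-correct share under independence is 0.9⁶ = 53%, and it can lie anywhere from 40% to 90% depending on how errors cluster within HCPs. With a latent correlation of 0.3 between questions, simulation gives 62%. Under independence, an 80% all-correct share needs 0.8^(1/6) = 96.3% correct on each question.

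**4. Chance of meeting each reading.** Simulation, n = 50, true knowledge 85% on each question, 10,000 runs. The 85% and the correlations are assumptions.

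| Reading | Independent | Correlation 0.3 |
|---|---|---|
| Composite point estimate ≥ 80% | 99% | 97% |
| Every question ≥ 80% | 47% | 53% |
| All six correct in ≥ 80% of HCPs | 0% | 0% |
| Lower limit of composite (n = 50) ≥ 80% | 3% | 8% |

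**The case against.** The strongest reply is that only one rule was meant. The weighted composite appears throughout the protocol. Section 9.9.1.2 can be read as supplying the weight for the 9.2.1 composite if item means question. The all-questions wording stands in one synopsis sentence, where it is joined to a weighted average, which makes no sense for an all-correct share. The same part of the synopsis also gives the criterion as a weighted percentage of correct responses. The synopsis is labelled 07 June 2021, V 0.2, inside a protocol of version 2.0, so the sentence may be a leftover. Because respondents advance only as they complete each question, the different counts of 30 should seldom diverge much.

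Most of this stands as an account of how the conflict arose, and it points to the weighted average as the intended rule. It does not remove the conflict: the synopsis is part of the current protocol, and the loose item wording and the undefined ± 95% CI are in the body as well.

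A reader might go further in three ways that the document does not support.

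- Table 9-1, which scores single response options, might be taken as another rival definition. It lists collected variables and states no success rule. As available here it shows 20 knowledge rows, only three of them for question 8, while Annex 3 has six options for that question. The table looks broken in reading, so nothing should be computed from its row count.
- One might infer that the choice of rule will be made after seeing results. The SAP is to be final before data collection ends (synopsis, 9.3) or before database close (9.9.1), and nothing indicates an earlier look at results.
- One might speak of type I error or power. Section 8.2 states that there is no a priori hypothesis and the analyses are descriptive, so only the success verdict is affected.

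**Conclusion.** The point holds as an inconsistency in the current text that must be corrected. The firm contradiction is between the weighted average (8.1, 9.2.1, 9.9.1.2 and the endpoint part of the synopsis) and the all-questions-correct share in the synopsis analysis. The per-item success sentence and the unexplained ± 95% CI are ambiguities on top of it. It would go too far to count 9.9.1.2 as a further incompatible definition.

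In the illustrative data the verdict moves from 85.7% (pass) to at most 70% (fail). At 90% per question with independent answers, the figure set against 80% is either 90% or 53%. The individual percentages rest on assumed knowledge levels and correlations. Two results do not: an all-correct share is capped by the worst question, and the protocol's own planning case passes or fails according to the role given to the interval. An SAP could add detail, but it would have to override one protocol sentence to do so.

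**What to change.** State one rule in the synopsis, 9.2.1 and 9.9.1.2:

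- The composite is the denominator-weighted average of the six question-level percentages correct, keeping the weighting that 9.9.1.2 already specifies. Equal weighting is not needed.
- Replace item with question throughout, and give one rule for when a multi-option question (3, 6, 7, 8) counts as correct. The choice of scoring rule is the sponsor's.
- Success is a composite point estimate of at least 80%, with the 95% CI reported descriptively.
- Count the minimum of 30 HCPs in one stated way.
- In the decision sentences, delete the reference to all the questions and the bracketed ± 95% CI, and refer to the primary endpoint in the singular.
- Report the all-six-correct percentage as supportive.

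The cost is protocol wording in those places, carried into the SAP before it is finalised. No new data or change to the questionnaire is needed.
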